11.3. Appendix 3: Assessment Windows

11.3.1. Definitions of Assessment Windows for Efficacy Analyses

Analysis Set / Domain	Parameter (if applicable)	Target Number of Days from Day 1 in each TC	Analysis Window		Analysis Timepoint
			Beginning Timepoint	Ending Timepoint	
e.g. "Safety", "Efficacy" or list specific domains if required	e.g. "All" or list specific parameters (i.e. tests) if required	The target or most desired relative day or relative time value for a given visit. e.g. "Day 7"	e.g. "Day 1"	e.g. "Day 10"	e.g. VISIT 1
Efficacy		Study Baseline		Day 1 [1]	Study Baseline
Efficacy		Day 15	Day 2	Day 29	TC1 Week 2
Efficacy		Day 43	Day 30	Day 64	TC1 Week 6
Efficacy		Day 85	Day 65	Day106	TC1 Week 12
Efficacy		Day 127	Day 107	Day 148	TC1 Week 18
Efficacy		Day 169	Day149	Day190	TC1 Week 24
Efficacy		Day 211	Day191	Day 232	TC1 Week 30
Efficacy		Day 253	Day 233	Day 274	TC1 Week 36
Efficacy		Day 295	Day 275	Day 316	TC1 Week 42
Efficacy		Day 337	Day 317	Day 358	TC1 Week 48
Efficacy		Day 1	Latest pre-dose assessment before 2 nd treatment [2]		TC2 Week 0
Efficacy		Day 15	Day 2	Day 29	TC2 Week 2
Efficacy		Day 43	Day 30	Day 64	TC2 Week 6
Efficacy		Day 85	Day 65	Day106	TC2 Week 12
Efficacy		Day 127	Day 107	Day 148	TC2 Week 18
Efficacy		Day 169	Day149	Day190	TC2 Week 24
Efficacy		Day 211	Day191	Day 232	TC2 Week 30
Efficacy		Day 253	Day 233	Day 274	TC2 Week 36
Efficacy		Day 1	Latest pre-dose assessment before 3 rd treatment [2]		TC3 Week 0
Efficacy		Day 15	Day 2	Day 29	TC3 Week 2
Efficacy		Day 43	Day 30	Day 64	TC3 Week 6
Efficacy		Day 85	Day 65	Day106	TC3 Week 12
Efficacy		Day 127	Day 107	Day 148	TC3 Week 18
Efficacy		Day 169	Day149	Day190	TC3 Week 24

NOTES :

- [1] prior to treatment. If the date of assessment of efficacy endpoint is the same as the date of treatment, this can be regarded as prior to treatment according to study protocol.

Analysis Set / Domain	Parameter (if applicable)	Target Number of Days from Day 1 in each TC	Analysis Window		Analysis Timepoint
			Beginning Timepoint	Ending Timepoint	

- [2] typically to use data of qualification for re-treatment
- Day 1 is the treatment date in each TC

11.3.2. Definitions of Assessment Windows for Safety Analyses (only Week 48 visit and Withdraw visit)

Table below shows the assessment window which applied to safety data at week 48 visit and withdrawal visit. Safety data at week 48 visit or withdrawal visit will be used as data of the visit within an assessment window, only if safety data for the planed scheduled visit is missing.

This assessment window will not be applied to any safety data at other visits. This means safety data except for week 48 visit and withdrawal visit will be only used as visit collected in eCRF.

Note that as described in section section 8, safety data at last visit (typically, this is week 48 visit or withdrawal visit) will be also treated as study exit.

Rationale: For example, if a given subject receive 2nd treatment at week 36 after 1st treatment and complete study (i.e., complete week 48 visit), data for week 48 visit will be entered in “Week 48” page in eCRF, not in “Week 12 from 2nd treatment” page. In this case, data for week 12 from 2nd treatment seems to be missing in eCRF, but this is not true. This is the case for other situations. In order to summarize safety data at week 48 visit or withdrawal visit appropriately in a given TC or GTCs, this assessment window is needed.

Analysis Set / Domain	Parameter (if applicable)	Target Number of Days from Day 1 in each TC/GTC	Analysis Window		Analysis Timepoint in appropriate study phase (TC1 or GTCs)
			Beginning Timepoint	Ending Timepoint	
e.g. “Safety”, “Efficacy” or list specific domains if required	e.g. “All” or list specific parameters (i.e. tests) if required	The target or most desired relative day or relative time value for a given visit. e.g. “Day 7”	e.g. “Day 1”	e.g. “Day 10”	e.g. VISIT 1
Safety		Day 15	Day 12	Day 18	Week 2
Safety		Day 43	Day 36	Day 50	Week 6
Safety		Day 85	Day 78	Day 92	Week 12
Safety		Day 127	Day 120	Day 134	Week 18
Safety		Day 169	Day 162	Day 176	Week 24
Safety		Day 211	Day 204	Day 218	Week 30
Safety		Day 253	Day 246	Day 260	Week 36
Safety		Day 295	Day 288	Day 302	Week 42

Analysis Set / Domain	Parameter (if applicable)	Target Number of Days from Day 1 in each TC/GTC	Analysis Window		Analysis Timepoint in appropriate study phase (TC1 or GTCs)
			Beginning Timepoint	Ending Timepoint	
Safety		Day 337	Day 330	Day 343	Week 48

NOTES :

- Day 1 is the treatment date in each TC/GTC

11.4. Appendix 4: Study Phases and Treatment Emergent Adverse Events

11.4.1. Study Phases

Assessments and events will be classified according to time of occurrence relative to the start date of the study treatment and/or study withdraw date.

11.4.1.1. Study Phases for Efficacy Data

Treatment State	Definition
Pre-Treatment	Date \leq 1st treatment Date
Treatment Cycle 1 (TC1)	1st treatment Date < Date (if the subject completes /withdraws without 2nd treatment) \leq Study Exit/Withdraw Date or (if the subject take 2nd treatment) \leq 2nd treatment Date
Treatment Cycle 2 (TC2)	2nd treatment Date < Date (if the subject completes / withdraws without 3rd treatment) \leq Study Exit/Withdraw Date or (if the subject take 3rd treatment) \leq 3rd treatment Date
Treatment Cycle 3 (TC3)	3rd treatment Date < Date \leq Study Exit/Withdraw Date

NOTES:

- If the date of assessment of efficacy endpoint is the same as the date of 1st treatment, this can be regarded as prior to treatment according to study protocol.

11.4.1.2. Study Phases for AE Data

Treatment State	Definition
Pre-Treatment	AE Start Date < Study Treatment Start Date
On-Treatment	If AE onset date is on or after treatment start date & on or before treatment stop date. Study Treatment Start Date \leq AE Start Date \leq Study Treatment Stop Date
Onset Time Since 1st Dose (Days)	If Treatment Start Date > AE Onset Date = AE Onset Date - Treatment Start Date If Treatment Start Date \leq AE Onset Date = AE Onset Date - Treatment Start Date +1 Missing otherwise.
Duration (Days)	AE Resolution Date – AE Onset Date + 1
Treatment Cycle 1 (TC1) \leq 84 days from 1st treatment	1st treatment Date \leq AE Start Date \leq 1st treatment Date +83
Treatment Cycle 1 (TC1)	1st treatment Date \leq AE Start Date (if the subject completes / withdraws without 2nd treatment) \leq Study Exit/Withdraw Date or (if the subject take 2nd treatment) < 2nd treatment Date

Treatment State	Definition
GSK1358820 Treatment Cycle 1 (GTC1)	For subjects who received GSK1358820 as 1st treatment: 1st treatment Date \leq AE Start Date (if the subject completes / withdraws without 2nd treatment) \leq Study Exit/Withdraw Date or (if the subject take 2nd treatment) $<$ 2nd treatment Date For subjects who received placebo as 1st treatment: 2nd treatment Date / Time \leq AE Start Date / Time (if the subject completes / withdraws without 3rd treatment) \leq Study Exit/Withdraw Date or (if the subject take 3rd treatment) $<$ 3rd treatment Date
GSK1358820 Treatment Cycle 2 (GTC2)	For subjects who received GSK1358820 as 1st treatment: 2nd treatment Date / Time \leq AE Start Date / Time (if the subject completes / withdraws without 3rd treatment) \leq Study Exit/Withdraw Date or (if the subject take 3rd treatment) $<$ 3rd treatment Date For subjects who received placebo as 1st treatment: 3rd treatment Date / Time \leq AE Start Date / Time \leq Study Exit/Withdraw Date
GSK1358820 Treatment Cycle 3 (GTC3)	For subjects who received GSK1358820 as 1st treatment: 3rd treatment Date / Time \leq AE Start Date / Time \leq Study Exit/Withdraw Date For subjects who received placebo as 1st treatment: Not applicable because 3 rd treatment of GSK1358820 is not allowed for subjects who received placebo as 1st treatment
Overall	For subjects who received GSK1358820 as 1st treatment 1st treatment Date \leq AE Start Date \leq Study Exit/Withdraw Date For subjects who received placebo as 1st treatment 2nd treatment Date \leq AE Start Date \leq Study Exit/Withdraw Date

NOTES:

- If the study withdraw date is missing then the AE will be considered to be On-Treatment.

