### **6.1.2.3. Treatment Procedure**

A flexible or rigid cystoscope may be used for study treatment administration. The bladder should be instilled with a sufficient amount of saline in order to achieve adequate visualization for the study injections.

[figure not shown]
The investigator (or subinvestigator) will prepare three 10 mL syringe pre-filled with 30 mL of study medication and one 1 mL syringe pre-filled with saline. The 30 mL of study drug will be administered as 30 injections each of 1.0 mL. Under direct cystoscopic visualization, injections should be distributed evenly across the detrusor wall and spaced approximately 1 cm apart. To avoid injecting the trigone or bladder dome the injections should be at least 1 cm above the trigone and approximately 3 cm below the dome. The injection needle should be inserted approximately 2 mm into the detrusor for each injection. For the final injection site, a sufficient amount of saline (from the 1 mL syringe) will be flushed through the injection needle to deliver the small amount of study medication remaining in the needle. This will ensure that the entire volume of study medication is delivered to the patient. After the injections are given, the saline used for bladder wall visualization should be immediately drained.

Indwelling catheters may be used during the 24 hour post treatment period at the discretion of the investigator(or subinvestigator).

All patients must be observed for at least 30 minutes following the study treatment administration. Safety monitoring and assessments are to be done according to local site practice (e.g. monitoring of blood pressure, pulse rate and, for patients with the ability to spontaneously void, ensuring that patient has emptied the bladder before leaving the site).

Spinal cord injury patients with lesions above the T6 level are particularly at risk of developing autonomic dysreflexia, which presents with symptoms of increased blood pressure, relative bradycardia, headache, and skin flushing [Blackmer, 2003; Paralyzed Veterans of

America/Consortium for Spinal Cord Medicine, 2001]. Should autonomic dysreflexia develop in a patient, the condition should be immediately handled according to local site practice. An occurrence of autonomic dysreflexia during study drug administration will be reported as an adverse event. Prior to leaving the study clinic, patients will be instructed to contact the study site if they experience any adverse events post-treatment.

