8.1. Adverse Events Analyses

Adverse events analyses including the analysis of adverse events (AEs), Serious (SAEs) and other significant AEs will be based on GSK Core Data Standards. The details of the planned displays are provided in [Appendix 10: List of Data Displays](#).

All AEs will be classified using the standard GSK Medical Dictionary for Regulatory Activities (MedDRA) dictionary, and grouped by SOC and PT, unless otherwise stated. The investigator will evaluate all AEs with respect to seriousness, severity, and causality.

AEs analyses will be by treatment group (and total for GTC1, GTC2, GTC3 and Overall) and study phases (i.e., TC1, TC1 <= 84 days, GTC1, GTC2, GTC3 and Overall, see section [11.4](#)). Note that Overall includes all AEs after GSK1358820 treatment.

The number and percentage of subjects experiencing an AE and the total number of AEs (the number of subjects with any AEs) will be summarized for each of the following AE categories by treatment group (and total for GTC1, GTC2, GTC3 and Overall):

- All AEs (by SOC and PT; by SOC and PT and maximum severity)
- Serious AEs (by SOC and PT)
- Treatment related AEs (by SOC and PT; by SOC and PT and maximum severity)

- Study drug related AEs (by SOC and PT; by SOC and PT and maximum severity)
- Injection related AEs (by SOC and PT; by SOC and PT and maximum severity)
- Serious treatment related AEs (by PT, for PLS)
- Non-serious treatment related AEs (by PT, for PLS)

The tabular summary for each category of AE listed above will include the number of subjects who reported at least one event, and percentage of subjects who reported at least one AE (incidence) by treatment group (and total for GTC1, GTC2, GTC3 and Overall) for each SOC (where applicable), each PT, and overall. By default, adverse events will be sorted by MedDRA SOCs, in descending order from the SOC with the highest total incidence (i.e., summed across all treatment groups) for any adverse event within the class, to the SOC with the lowest total incidence. If the total incidence for any two or more adverse events is equal, the events will be presented in alphabetical order. Only SOCs with observed AE PTs will be presented. Repeat sort order for MedDRA PTs within each SOC.

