11.7.2.1. Handling of Missing and Partial Dates

Element	Reporting Detail
General	
 • Partial dates will be displayed as captured in subject listing displays.
Adverse Events	
 • The eCRF does not allow for the possibility of partial dates (i.e., only month and year) to be recorded for AE start and end dates • Completely missing start or end dates will remain missing, with no imputation applied. Consequently, time to onset and duration of such events will be missing. For example, this is the case for AEs status of ‘ongoing’ or AEs in interim analyses.
Concomitant Medications/ Medical History/NDO history	
 • Partial dates for any concomitant medications recorded in the CRF will be imputed using the following convention: 
 ○ If the partial date is a start date, a '01' will be used for the day and 'Jan' will be used for the month ○ If the partial date is a stop date, a '28/29/30/31' will be used for the day (dependent on the month and year) and 'Dec' will be used for the month. • The recorded partial date will be displayed in listings.

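### Adverse-event cycles close on a date but reopen on a date and time, so an event on a re-treatment day before the injection may belong to no cycle

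*SAP*

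**What the plan says.** SAP 11.4.1.2 defines the phases. TC1 is the double-blind cycle, and GTC1 to GTC3 are the successive cycles on GSK1358820. When a second injection is given, TC1 (and GTC1 for subjects who had GSK1358820 first) ends on date alone: "if the subject take 2nd treatment) < 2nd treatment Date". The cycle before a third injection ends in the same way, strictly before the third treatment date.

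The cycles that open at a re-treatment are written on a finer scale. At the second injection (GTC2 for GSK-first subjects, GTC1 for placebo-first subjects) the injection's date and time are compared with "AE Start Date / Time (if the subject completes / withdraws without 3rd treatment". At the third injection (GTC3 for GSK-first, GTC2 for placebo-first) the lower limit is "3rd treatment Date / Time". TC1, GSK-first GTC1 and Overall open on date alone.

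SAP 8.1 reports AEs by "study phases (i.e., TC1, TC1 <= 84 days, GTC1, GTC2, GTC3 and Overall, see section" 11.4, with no other phase to catch a remainder. It also states: "Note that Overall includes all AEs after GSK1358820 treatment". Section 8 presents GTC1 by treatment group and in total. On data handling, SAP 11.7.2.1 says of AE start and end dates: "The eCRF does not allow for the possibility of partial dates". It has no rule for a missing AE time.

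**The concern.** A strict date limit on one side and a date/time limit on the other leave the early part of each re-treatment day in no cycle. Study procedures do take place in those hours. Protocol 6.1.2.2 provides for anesthetic instillation held in the bladder for at least 15 minutes, for sedation and for general anesthesia. Protocol 6.1.2.3 requires bladder filling and cystoscopy before the needle is used.

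The by-cycle tables for repeat dosing are at stake: all AEs, treatment-, drug- and procedure-related AEs, serious AEs and events of special interest (SAP Tables 3.18 to 3.44 and 3.58 to 3.66, with the related plain-language tables). Safety of repeated dosing is a stated objective. GTC1 also has a total column that pools GSK-first subjects, whose cycle opens on date, with placebo-first subjects, whose cycle opens on date and time.

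**Working it through.** There is no planned figure to reproduce; this is a check of interval edges. D2, D3 are the calendar dates of the 2nd and 3rd injections and T2, T3 their date/times.

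| Cycle | Subjects | Opens | Closes if re-treated |
|---|---|---|---|
| TC1 | both groups | AE date ≥ 1st treatment date | AE date < D2 |
| GTC1 | GSK-first | AE date ≥ 1st treatment date | AE date < D2 |
| GTC1 | placebo-first | AE date/time ≥ T2 | AE date < D3 |
| GTC2 | GSK-first | AE date/time ≥ T2 | AE date < D3 |
| GTC2 | placebo-first | AE date/time ≥ T3 | study exit |
| GTC3 | GSK-first | AE date/time ≥ T3 | study exit |
| Overall | GSK-first / placebo-first | AE date ≥ 1st treatment date / ≥ D2 | study exit |

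**Test events, rules read literally.** Take injections at 10:00.

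- *AE at 08:00 on D2.* AE date < D2 is false, so the earlier cycle rejects it. AE date/time ≥ T2 is false, so the new cycle rejects it. Overall accepts it. D3 gives the same result. Two groups by two re-treatments make 4 cases, and all 4 fall in no cycle.
- *AE on the day before D2 or D3.* Assigned to the earlier cycle.
- *AE at 12:00 on D2 or D3.* Assigned to the new cycle.
- *AE at 08:00 on the first treatment day.* Counted in TC1, and also in GTC1 for GSK-first subjects. This applies to an event recorded as an AE: Protocol 7.4.1.1 starts AE collection at study treatment and lets earlier occurrences go to medical history.

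**The same events with date-only starts.** None of the 4 cases is unassigned; each goes to the cycle opened that day.

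**The 84-day window.** It ends at the 1st treatment date + 83. Re-treatment requires at least 84 days to have elapsed (Protocol 5.3), so no re-treatment day lies inside it.

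**Comparable definitions.** The efficacy phases in SAP 11.4.1.1 close at ≤ the next treatment date and open at > that date, which leaves no gap. Follow-up time in SAP 11.6.2 ends on the day before re-treatment and restarts on the re-treatment date, so the whole day already counts as follow-up of the new cycle.

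**Size.** The most re-treatment days possible is 30 × 2 = 60. One subject is 1/15 = 6.7 percentage points in a group of 15. If a cycle held 10 subjects (an assumption), it would be 1/10 = 10 points.

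**The case against.** The strongest reply is that the gap needs AE clock times, and the documents never say that these are collected. The other AE evidence is at date level: SAP 11.4.1 classifies by start date, 11.4.1.2 derives onset and duration in days from dates, 11.7.2.1 deals only with dates, and Appendix 12 cuts AE data on a date variable. SAP 11.6.3 does use the injection time, but for diary episodes, whose times the diary records. If AEs carry dates only, the date/time starts collapse to date-only starts and the gap vanishes. This stands as a limit on the impact. It does not rescue the text, which would then call for a variable that does not exist.

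Several stronger readings are tempting and are not supported:

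- **That every re-treatment is affected.** Sixty is a ceiling on dosing days, not a count of events. An event must start on that day and before the injection.
- **That procedure-related events generally fall in the gap.** The protocol's statement on autonomic dysreflexia, "An occurrence of autonomic dysreflexia during study drug administration will be reported as an adverse event", concerns events during administration. An onset at or after the recorded injection time enters the new cycle. Nothing in the documents shows that onsets cluster just before it.
- **That events vanish.** They remain in the Overall tables (3.45 to 3.52, 3.67 and 3.68) and in the AE listings.
- **That a failure of cycle counts to sum to Overall is itself evidence of error.** The Overall tables count subjects, and subject counts need not sum across cycles.
- **That a first-versus-repeat comparison is biased.** No such test is planned, and the study evaluates no formal hypotheses.

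**Conclusion.** The defect is real and small. As written, SAP 11.4.1.2 either leaves same-day pre-injection events out of every cycle or cannot be executed, depending on whether AE onset times exist. No note in SAP 11.4 or 11.7 repairs it. The date-only starts of TC1, GSK-first GTC1 and Overall, and the matching edges of the efficacy phases, suggest that consistent bounds were intended.

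The by-cycle loss rests on onset times being recorded and used. The shift of 6.7 to 10 points also requires that the subject has no other event of the same term in that cycle, because the tables count subjects with at least one event. Few events are likely to be affected, and the randomized comparison up to 84 days is not. A reader might infer that repeat-dose safety is materially understated; the documents do not support that. They support correcting the definition before the cycle tables are programmed.

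**What to change.** Use one resolution at both edges of every AE cycle. The simplest edit is a date-only start (treatment date ≤ AE start date) for placebo-first GTC1, for GTC2 in both groups and for GTC3. This fits the existing closing limits, the TC1 and Overall starts and the follow-up rule in SAP 11.6.2. Each AE with a start date from the first treatment to study exit then falls in one interval between injections. TC1 and GTC1 still coincide for GSK-first subjects, as designed.

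The cost is a short SAP edit and a small programming change. SAP Appendix 10 schedules the GTC tables for the final report only, so the planned interim tables do not change.

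There is a small downside. A same-day pre-injection event is assigned to the dose that follows it. For placebo-first subjects this includes an event before their first GSK1358820 injection, which would enter GTC1. The date-only Overall definition already does this, despite the description in SAP 8.1 of Overall as events after GSK1358820 treatment. The SAP should state the convention.

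The alternative is date and time at both edges, which leaves such an event in the previous cycle. It requires AE onset times and a rule for when they are missing, and the SAP has neither.

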11.4.1.3. Study Phases for Concomitant Medication

Study Phase	Definition
Prior	If medication end date is not missing and is before the first treatment date
Concomitant	Any medication that is not a prior

NOTES:

- Please refer to [Appendix 7: Reporting Standards for Missing Data](#) for handling of missing and partial dates for concomitant medication. Use the rules in this table if concomitant medication date is completely missing.
- The definition of "prior" for prior NDO medication is different from above definition, in accordance with study protocol.

11.4.2. Treatment Emergent Flag for Adverse Events

Treatment emergent flag for AEs is not defined in this study.

11.5. Appendix 5: Data Display Standards & Handling Conventions

11.5.1. Reporting Process

Software	

 The currently supported versions of SAS software will be used. 	
Reporting Area	
HARP Server	: US1SALX00259
HARP Compound	[for interim analyses]: arenv/arprod/gsk1358820/mid204948/primary [for final analyses]: arenv/arprod/gsk1358820/mid204948/final
Analysis Datasets	

 Analysis datasets will be created according to Legacy GSK A&R dataset standards. . 	
Generation of RTF Files	

 RTF files will not be generated. 	

11.5.2. Reporting Standards

General

 The current GSK Integrated Data Standards Library (IDSL) will be applied for reporting, unless otherwise stated (IDSL Standards Location: https://spope.gsk.com/sites/IDSLLibrary/SitePages/Home.aspx): 
 4.03 to 4.23: General Principles 5.01 to 5.08: Principles Related to Data Listings 6.01 to 6.11: Principles Related to Summary Tables 7.01 to 7.13: Principles Related to Graphics Do not include subject level listings in the main body of the GSK Clinical Study Report. All subject level listings should be located in the modular appendices as ICH or non-ICH listings
Formats

 GSK IDSL Statistical Principles (5.03 & 6.06.3) for decimal places (DP's) will be adopted for reporting of data based on the raw data collected, unless otherwise stated. Numeric data will be reported at the precision collected on the eCRF. The reported precision from non eCRF sources will follow the IDSL statistical principles but may be adjusted to a clinically interpretable number of DP's.
Planned and Actual Time

 Reporting for tables, figures and formal statistical analyses: 
 Planned time relative to dosing will be used in figures, summaries, statistical analyses and calculation of any derived parameters, unless otherwise stated. The impact of any major deviation from the planned assessment times and/or scheduled visit days on the analyses and interpretation of the results will be assessed as appropriate. Reporting for Data Listings: 
 Planned and actual time relative to study drug dosing will be shown in listings (Refer to IDSL Statistical Principle 5.05.1). Unscheduled or unplanned readings will be presented within the subject's listings.
Unscheduled Visits

 Unscheduled visits will not be included in summary tables and/or figures. All unscheduled visits will be included in listings.

Descriptive Summary Statistics	
Continuous Data	Refer to IDSL Statistical Principle 6.06.1 N, mean, standard deviation (or standard error), median, minimum, maximum.
Categorical Data	N, n, frequency, %
Graphical Displays	

• Refer to IDSL Statistical Principals 7.01 to 7.13.	

